Days Assessments ⁵	-28 to -1	Predose	Dosing/Postdose	(24 ±1 h) postdose	8 (±2)	15 (±3)	16 (+1) ⁴	22 (±3)	29 (±3)	30 (+1) ⁴	36 (±3)	50 (±3)	57, 85, 113, 141 (±3)	114, 142	148	78, 106, 134, 162 (±3)	169 (±3) ³	170 (+1) ⁴	176 (±3)	177 (+1) ⁴	214 (±3)	215 (+1) ⁴	259 (±3)	260 (+1) ⁴	UV
HHD ²¹		X							X				X				X				х		X		
Randomization/ Admission to Inpatient Facility		X																							
Study Treatment Administration ²³			X			X			X				X				X								
C-SSRS Questionnaire ²⁴		X			X	X		X	X		X		X		X		X		X		X		X		X

																					FU Per	riod ²	1		
	Screening ¹	Dose 1 (I	npati	ent)	CV	Dose 2	тс	CV	Dose 3	тс	CV	TC	Doses 4, 5, 6, 7	тс	CV	тс	Dose 8	тс	CV	тс	cv	тс	Final/ ET Visit	тс	
Days Assessments ⁵	-28 to -1	Predose	Dosing/Postdose	(24 ±1 h) postdose	8 (±2)	15 (±3)	16 (+1) ⁴	22 (±3)	29 (±3)	30 (+1)4	36 (±3)	50 (±3)	57, 85, 113, 141 (±3)	58, 86, 114, 142 (+1) ⁴	64, 92, 120, 148 (±3)	78, 106, 134, 162 (±3)	169 (±3) ³	170 (+1) ⁴	176 (±3)	177 (+1) ⁴	214 (±3)	215 (+1) ⁴	259 (±3)	260 (+1) ⁴	UV
Clinical Laboratory Samples for Hematology, Coagulation, Blood Chemistry, and Urinalysis ²⁵	X	Х		X		X			X		Х		X		X		X		X		Х		X		
Serum Sampling for PK ²⁶		X	X	X	X	X			Х				X				X		X						
Blood Sampling for Biomarkers ²¹		X							Х				X				X				Х		X		
CSF Sampling ²⁹		X				X			X				X				X		X ³⁰		X		X		

																					FU Per	riod ²			
	Screening ¹	Dose 1 (I	(npati	ient)	CV	Dose 2	TC	CV	Dose 3	TC	CV	тс	Doses 4, 5, 6, 7	тс	CV	тс	Dose 8	тс	CV	тс	CV	тс	Final/ ET Visit	тс	
Days		1		2	8 (±2)	15 (±3)		22 (±3)	29	30 (+1) ⁴	36	50	57,	58, 86,	64, 92,	78, 106,	169 (±3) ³	170 (+1) ⁴	176 (±3)	177 (+1) ⁴	214 (±3)	215 (+1) ⁴	259	260 (+1) ⁴	
Assessments ⁵	-28 to -1	Predose	Predose 113, 114, 120, 134, 162 (±3) (±3) (±3) UV X																						
Discharge From Inpatient Facility				X																					
Concomitant Therapy and Procedures Recording		X																							
AE Recording														X											
SAE Reporting		X X																							

¹ Screening assessments can be performed on multiple days (up to 7 days) for ease of participant burden.

² Participants in Cohorts D1 and D2 who enter Part 2 after their Treatment Period (after the Day 176 Visit) will not be required to complete the follow-up visits in Part 1 that occur after their enrollment in Part 2. Participants from Cohorts D1 and D2 who do not enter Part 2 will have two follow-up clinic visits and two TCs approximately 6 and 12 weeks after their last dosing visit.

³ The Part 1 Day 169 Visit may serve as the start of screening period for Part 2. Results from Part 1 Day 169 and Day 176 Visit assessments may be used for the purpose of screening and do not need to be repeated, as long as they are conducted within one month of the Part 2 Day 1 Visit.

⁴ TCs that are scheduled for the day after an LP are only required if LP was performed on the previous day.

⁵ All clinic visits are expected to take place on site unless participants are unable to travel to the site due to a public health emergency (see Section 16.6)

⁶ An informant/caregiver should be available at Screening, and the participation of the same informant/ caregiver for the duration of the study. The informant/ caregiver must provide written informed consent to participate in the study prior to providing any information on either themselves and/or participants.

 $^{^{7}}$ Including blood samples for HIV, HCV, and hepatitis B virus.

 $^{^{\}rm 8}$ For women of child bearing potential only; to be performed centrally.

A Phase 1/2 MAD Study and Long-Term OLE in Adults With ALS With or Without ATXN2 PolyCAG Expansion

¹⁵ During UV, ECGs are to be done if medically indicated. All ECGs will be read by the Investigator at collection and then sent to a central ECG reader for further evaluation and to confirm eligibility at Screening.

	4h
¹⁶ Assessments completed on the mobile device include	the participant ventilation diary. The participant should complete
	s on the mobile device after Day 1 will be completed on a weekly basis and may be
completed at home. Participants should be encouraged to bring the device	e with them to each study visit.

⁹ Performed predose on dosing days for women of childbearing potential only; to be performed locally.

¹⁰ To be conducted only in female participants presenting with a history of being postmenopausal to confirm postmenopausal status.

¹¹ Limited physical examination from Day 8 to Day 259 and UV per the Investigator's discretion.

¹² On dosing days, to be assessed predose and at 3 and 6 hours postdose (±15 minutes). At UV, a limited neurological examination may be performed per the Investigator's discretion.

¹³ Day 92 CV only.

¹⁴ On dosing days, ECG and vital signs are to be assessed just prior to drawing PK blood samples at predose, and 2 and 4 hours postdose (±15 minutes). Vital signs may be measured in either the sitting or supine position, and ECGs are to be done in triplicate after resting in the supine position (or semi-recumbent position, if supine is not possible) for ≥ 5 minutes.

¹⁹ On Day 1, the participant should complete the ventilation diary in clinic and enter ventilation data for the week prior (i.e., for Days -7 to -1) into the diary on the mobile device. After Day 1, the participant will complete the ventilation diary on the mobile device on a weekly basis.

²⁰ Study staff should review the participant's ventilation diary with the participant. If there are missing data or discrepancies, the site may document their conversation with the participant as source to supplement the ventilation diary data. For dosing visits, this procedure may be completed up to 24 hours prior to dosing except on Part 1 Day 1, when it should be completed on the dosing day.

²¹ When required on dosing days, assessment to be done predose. SVC, and HHD may be collected up to 24 hours prior to dosing.

²²Refers to the ALSFRS-R that is administered by a certified evaluator. The evaluator should be blinded to the participant's treatment assignment and to the results of other assessments. To be performed before dosing; may be performed up to 24 hours prior to dosing except on Part 1 Day 1, when it should be administered on the dosing day.

²³ Administered by LP.

²⁴ Use "Since Last Visit" version of C SSRS from Day 8 onward. At UV may be assessed per the Investigator's discretion.

²⁵ On dosing days, to be collected before dosing. HbA1c and lipid panel to be assessed at Screening and on Days 1, 85, 176, and 259 only.

²⁶ To be collected predose and at 1, 2, 4, and 6 hours (±15min) postdose on dosing days.

²⁷ On Day 85 Visit only.

A Phase 1/2 MAD Study and Long-Term OLE in Adults With ALS With or Without ATXN2 PolyCAG Expansion

29 To be collected predose on dosing days. Collected by LP.

Participants to be observed in the clinic for ~6 hours after the LP procedure on dosing days and for ~1 hour on nondosing days.

³⁰ This LP is only done if participant is not entering LTE.

Table 3: Schedule of Activities Part 2 (all Cohorts)

		Loading Dose Perio	od					Maintenance l	Dose Period	Follov	v Up Peri	od		
	Screening ¹	Dose 1	тс	Dose 2		Dose 3	тс	Maintenance Dose Visit	тс	CV	тс	Final/ ET Visit	тс	-
Days Assessments ²	-28 to -1	1 (±3)	2 (+1) ³	15	16 (+1) ³	29	30 (+1) ³	57, 85, 113, 141, 169, 197, 225, 253, 281, 309, 337, 365, 393, 421, 449, 477, 505, 533, 561, 589, 617, 645, 673, 701, 729, 757, 785, 813, 841, 869, 897, 925, 953, 981, 1009, 1037, 1065, 1093 (±3)	1 day after each maintenance dose visit	45d after last dose (+/-3)	1 day after Follow- up CV (+1) ³	90d after last dose (+/-3)	1 day after Final/ETV (+1) ³	UV
ICF (Main)	X													
ICF (Informant/ Caregiver)	X													
Confirmation of Eligibility Criteria	X													
Medical History	X	X												
Clinical Laboratory Samples for Viral Serology ⁴	X													
Serum Pregnancy Test ⁵	X													

		Loading Dose Perio	od					Maintenance I	Dose Period	Follov	v Up Peri	od		
	Screening ¹	Dose 1	TC	Dose 2	TC	Dose 3	TC	Maintenance Dose Visit	TC	CV	TC	Final/ ET Visit	TC	
Days Assessments ²	-28 to -1	1 (±3)	2 (+1) ³	15 (±3)	16 (+1) ³	29 (±3)	30 (+1) ³	57, 85, 113, 141, 169, 197, 225, 253, 281, 309, 337, 365, 393, 421, 449, 477, 505, 533, 561, 589, 617, 645, 673, 701, 729, 757, 785, 813, 841, 869, 897, 925, 953, 981, 1009, 1037, 1065, 1093 (±3)	maintenance dose visit (+1) ³	45d after last dose (+/-3)	1 day after Follow- up CV (+1) ³	90d after last dose (+/-3)	1 day after Final/ETV (+1) ³	UV
Urine Pregnancy Test ⁶		X		X		X		X		X		X		
FSH Test ⁷	X													
Physical Examination ⁸	X	X		X		X		X		X		X		X
Neurological Examination (cranial nerves, cerebellar function, motor, and reflexes) ⁹	X	X		X		X		X		Х		Х		X
Weight	X	X						X ¹⁰				X		
Height	X													

225, 253, 281, maintenance dose visit (+1) ³ last dose (+/-3) (17)			Loading Dose Perio	od			Maintenance I	Dose Period	Follov	v Up Peri	od		
(±3) (±3) (±1) (±3) (±3) (±1) (±3) (±3) (±1) (±3) (Screening ¹	Dose 1	TC				тс	CV	тс	ET	TC	-
Vital Signs X X X X X X X X X X X X X X X X X X X		-28 to -1		2 (+1) ³	15 (±3)	29 (±3)	141, 169, 197, 225, 253, 281, 309, 337, 365, 393, 421, 449, 477, 505, 533, 561, 589, 617, 645, 673, 701, 729, 757, 785, 813, 841, 869, 897, 925, 953, 981, 1009, 1037, 1065,	each maintenance dose visit (+1) ³	after last	after Follow-	after last dose	Final/ETV	UV
(temperature, blood pressure, heart rate,	12-Lead ECG ¹¹	X	X		X	X	X		X		X		X
	(temperature, blood pressure, heart rate,	Х	X		X	X	X		X		X		X
Set up study mobile device for Part 2 ¹³			X										

		Loading Dose Perio	d					Maintenance I	Dose Period	Follow	v Up Peri	od		
	Screening ¹	Dose 1	тс	Dose 2		Dose 3	TC	Maintenance Dose Visit	тс	CV	TC	Final/ ET Visit	TC	
Days Assessments ²	-28 to -1	1 (±3)	2 (+1) ³	15 (±3)	16 (+1) ³	29 (±3)	30 (+1) ³	57, 85, 113, 141, 169, 197, 225, 253, 281, 309, 337, 365, 393, 421, 449, 477, 505, 533, 561, 589, 617, 645, 673, 701, 729, 757, 785, 813, 841, 869, 897, 925, 953, 981, 1009, 1037, 1065, 1093 (±3)	maintenance dose visit	45d after last dose (+/-3)	1 day after Follow- up CV (+1) ³	90d after last dose (+/-3)	1 day after Final/ETV (+1) ³	UV
Participant Ventilation Diary ¹⁶					O	ngoing	g week	ly collection						
Review ventilation use ¹⁷		X		X		X		X		X		X		
ALSFRS-R (standard) ¹⁸	X	X		X		X		X		X		X		

225, 283, 281, maintenance dose visit ap CV (+/-3) (+/-3) (1/-3)			Loading Dose Perio	d					Maintenance I	Dose Period	Follov	v Up Peri	od		
Days 1 (±3) 2 (+1) ³ 15 (±3) 16 (29 (±3) (+1) ³ 17 (+1) ³ 2 (+1) ³ 2 (+1) ³ 18 (±3) 19 (±3) 10 (+1) ³ 11 (10,9,197, 225, 253, 281, 309, 337, 365, 365, 390, 617, 645, 673, 701, 729, 757, 785, 813, 841, 869, 897, 925, 953, 981, 1009, 1037, 1065, 1093 (±3) 10 (±3) 11 (day after each after follow-last dose (+1) ³ 10 (±1) ³ 11 (day after each after (+1) ³ 10 (±1) ³ 11 (day after each after (+1) ³ 11 (±3) 12 (±1) ³ 13 (±3) 14 (±3) 15 (±3) 16 (±3) 17 (±3) 18 (±3) 18 (±3) 19 (±1) ³ 19 (±1) ³ 10 (±1) ³ 10 (±1) ³ 11 (day after each after (+1) ³ 25 (51, 589, 617, 645, 673, 701, 729, 757, 785, 813, 841, 869, 897, 925, 953, 981, 1009, 1037, 1065, 1093 (±3) 10 (±1) ³ 11 (day after each after (+1) ³ 11 (day after each after (+1) ³ 19 (±1) ³ 10 (±1) ³ 10 (±1) ³ 11 (day after each after (+1) ³ 10 (±1) ³ 11 (day after each after (+1) ³ 10 (±1) ³ 10 (±1) ³ 10 (±1) ³ 11 (day after each after (+1) ³ 25 (53, 281, 30) 26 (±1) ³ 10 (±1) ³ 10 (±1) ³ 11 (day after each after (+1) ³ 27 (±1) ³ 28 (±1) ³ 29 (±1) ³ 20 (±1) ³ 20 (±1) ³ 20 (±1) ³ 21 (±1) ³ 22 (±1) ³ 23 (±1) ⁴ 25 (±1) ³ 26 (±1) ³ 27 (±1) ³ 28 (±1) ³ 29 (±1) ³ 20 (±1) ³ 20 (±1) ³ 21 (±1) ³ 22 (±1) ³ 23 (±1) ⁴ 24 (±1) ³ 25 (±1) ³ 26 (±1) ³ 27 (±1) ³ 28 (±1) ³ 29 (±1) ³ 20 (±1) ³ 20 (±1) ³ 20 (±1) ³ 21 (±1) ⁴ 22 (±1) ³ 23 (±1) ⁴ 24 (±1) ³ 25 (±1) ³ 26 (±1) ³ 27 (±1) ³ 28 (±1) ³ 29 (±1) ³ 20 (±1) ³ 21 (±1) ³ 21 (±1) ³ 22 (±1) ³ 23 (±1) ⁴ 24 (±1) ³ 25 (±1) ³ 26 (±1) ³ 27 (±1) ³ 28 (±1) ³ 29 (±1) ³ 20 (±1) ³ 21 (±1) ³ 22 (±1) ³ 23 (±1) ³ 24 (±1) ³ 25 (±1) ³ 26 (±1) ³ 27 (±1) ³ 28 (±1) ³ 29 (±1) ³ 20 (±		Screening ¹	Dose 1	тс						тс	CV	тс	ET	тс	
VC ¹⁹		-28 to -1	1 (±3)		15	16	29	30	57, 85, 113, 141, 169, 197, 225, 253, 281, 309, 337, 365, 393, 421, 449, 477, 505, 533, 561, 589, 617, 645, 673, 701, 729, 757, 785, 813, 841, 869, 897, 925, 953, 981, 1009, 1037, 1065,	1 day after each maintenance dose visit	45d after last dose	1 day after Follow- up CV	90d after last dose	1 day after Final/ETV (+1) ³	UV
VC ¹⁹ X X X X X X X X X	01/010														
	SVC ¹⁹	X	X		X		X		X		X		X		

		Loading Dose Perio	od					Maintenance I	Dose Period	Follov	v Up Peri	od		
	Screening ¹	Dose 1	тс	Dose 2	тс	Dose 3	тс	Maintenance Dose Visit	TC	CV	тс	Final/ ET Visit	TC	
Assessments ²	-28 to -1	1 (±3)	2 (+1) ³	15 (±3)	16 (+1) ³	29 (±3)	30 (+1) ³	57, 85, 113, 141, 169, 197, 225, 253, 281, 309, 337, 365, 393, 421, 449, 477, 505, 533, 561, 589, 617, 645, 673, 701, 729, 757, 785, 813, 841, 869, 897, 925, 953, 981, 1009, 1037, 1065, 1093 (±3)	maintenance dose visit	45d after last dose (+/-3)	1 day after Follow- up CV (+1) ³	90d after last dose (+/-3)	1 day after Final/ETV (+1) ³	UV
HHD ¹⁹		X						X^{10}				X		
Study Treatment Administration		X ²²		X		X		X						
C-SSRS Questionnaire ^{19, 23}		X		X		X		X		X		X		X
Clinical Laboratory Samples for Hematology, Coagulation, Blood Chemistry, and Urinalysis ²⁴	X	X		X		X		X		Х		X		
Serum Sampling for PK ¹⁹		X						X ²¹						

		Loading Dose Perio	od					Maintenance I	Dose Period	Follov	v Up Peri	od		
	Screening ¹	Dose 1	TC	Dose 2	TC	Dose 3	тс	Maintenance Dose Visit	TC	CV	тс	Final/ ET Visit	TC	-
Days Assessments ²	-28 to -1	1 (±3)	2 (+1) ³	15 (±3)	16 (+1) ³	29 (±3)	30 (+1)3	57, 85, 113, 141, 169, 197, 225, 253, 281, 309, 337, 365, 393, 421, 449, 477, 505, 533, 561, 589, 617, 645, 673, 701, 729, 757, 785, 813, 841, 869, 897, 925, 953, 981, 1009, 1037, 1065, 1093 (±3)	maintenance dose visit (+1) ³	45d after last dose (+/-3)	1 day after Follow- up CV (+1) ³	90d after last dose (+/-3)	1 day after Final/ETV (+1) ³	UV
Blood Sampling for Biomarkers ¹⁹		X				X		X		X		X		
CSF Sampling ²⁵		X		X		X		X		X		X		
Concomitant Therapy and Procedures Recording								Ongoing						X
AE Recording								Ongoing						X

		Loading Dose Perio	od					Maintenance l	Dose Period	Follov	v Up Peri	od		
	Screening ¹	Dose 1	TC	Dose 2	TC	Dose 3	TC	Maintenance Dose Visit	TC	CV	тс	Final/ ET Visit	TC	
Days Assessments ²	-28 to -1	1 (±3)	2 (+1) ³	15 (±3)	16 (+1) ³	29 (±3)	30 (+1) ³	57, 85, 113, 141, 169, 197, 225, 253, 281, 309, 337, 365, 393, 421, 449, 477, 505, 533, 561, 589, 617, 645, 673, 701, 729, 757, 785, 813, 841, 869, 897, 925, 953, 981, 1009, 1037, 1065, 1093 (±3)	maintenance dose visit (+1) ³	45d after last dose (+/-3)	1 day after Follow- up CV (+1) ³	90d after last dose (+/-3)	1 day after Final/ETV (+1) ³	UV
SAE Reporting					I	I		Ongoing						X

¹ For participants from Cohorts D1 and D2, the Part 1 Day 169 Visit may serve as the start of screening period for Part 2. Results from Part 1 Day 169 and Day 176 Visit assessments may be used for the purpose of screening and do not need to be repeated, as long as they are conducted within one month of the Part 2 Day 1 Visit.

² All clinic visits are expected to take place on site unless participants are unable to travel to the site due to a public health emergency (see Section 16.6).

³ TCs that are scheduled for the day after an LP are only required if LP was performed on the previous day.

⁴ Including blood samples for HIV, HCV, and hepatitis B virus.

⁵Only for participants from Cohorts A, B, C1, and C2. For women of childbearing potential only; to be performed centrally.

⁶ Performed predose on dosing days for women of childbearing potential only; to be performed locally

⁷ To be conducted only in female participants presenting with a history of being postmenopausal and whose postmenopausal status was not already confirmed in Part 1, to confirm postmenopausal status for Part 2.

⁸ Limited physical examination from Day 15 onward, and in UV, per the Investigator's discretion.

⁹ On dosing days, to be assessed predose and postdose. At UV, a limited neurological examination may be performed at the Investigator's discretion.

¹⁰ To be completed on Day 85, 169, 253, 337, 421, 505, 589, 673, 757, 841, 925, 1009, 1093 Visits only (i.e., every 12 weeks).

¹¹ ECGs to be assessed predose on dosing days. ECGs are to be done in triplicate after resting in the supine position (or semi-recumbent position, if supine is not possible) for ≥5 minutes. During UV ECGs are to be done if medically indicated. All ECGs will be read by the Investigator at collection and then sent to a central ECG reader for further evaluation and to confirm eligibility at Screening.

¹² Vital signs to be assessed both predose and postdose on dosing days. May be measured in either the sitting or supine position.

¹³ Participants from Cohorts D1 and D2 must bring their study mobile device to their Part 2 Day 1 visit. Participants from Cohorts A, B, C1, and C2 will receive their study mobile device on Part 2 Day 1. Assessments completed on the mobile device include ventilation diary. The participant should complete the first set of mobile device assessments for Part 2 in clinic on Part 2 Day 1. Assessments on the mobile device after Day 1 will be completed on a weekly basis and may be completed at home. Participants should be encouraged to bring the device with them to each study visit.

¹⁶ On Part 2 Day 1, the participant should complete the ventilation diary in clinic and enter ventilation data for the week prior (i.e., for Part 2 Days -7 to -1) into the diary on the mobile device. After Day 1, the participant will complete the ventilation diary on the mobile device on a weekly basis.

¹⁷ Study staff should review the participant's ventilation diary with the participant. If there are missing data or discrepancies, the site may document their conversation with the participant as source to supplement the ventilation diary data. For dosing visits, this procedure may be completed up to 24 hours prior to dosing except on Part 2 Day 1, when it should be completed on the dosing day.

¹⁸ Refers to the ALSFRS-R that is administered by a certified evaluator. For participants in Cohorts D1 and D2, during the blinded loading period, the evaluator should be blinded to the participant's treatment assignment and to the results of other assessments. To be performed before dosing; may be performed up to 24 hours prior to dosing, except on Part 2 Day 1, when it should be administered on the dosing day.

¹⁹ When required on dosing days, assessment to be done predose. prior to dosing. SVC, and HHD may be collected up to 24 hours

²¹ Only completed on Day 169, 337, 505, 673, 841, 1009 Visits (i.e., every 24 weeks).

²² Administered by LP. Participants must not receive their first dose in Part 2 less than 4 weeks after their last dose in Part 1.

²³ Participants from Cohorts D1 and D2 will use "Since Last Visit" version of C-SSRS on Day 1 onward. Participants from Cohorts A, B, C1, and C2 will use the "Since Last Visit" version of the C-SSRS from Day 15 onward. At UV may be assessed per the Investigator's discretion.

²⁴ On dosing days, to be collected before dosing. Lipid panel and HbA1c to be completed on Screening, Day 1, 85, 169, 253, 337, 421, 505, 589, 673, 757, 841, 925, 1009, 1093 Visits only (i.e., every 12 weeks).

²⁵ To be collected predose by LP on dosing days. Participants receiving 60mg dose to be observed in the clinic for ~1 hour after the LP procedure. Participants receiving 120mg dose to be observed in the clinic for at least 2 hours after the LP procedure.

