5.3.2. Dosing (Part 2)

Dosing in Part 2 will begin at the Sponsor's discretion. Prior to start of dosing, the SST must review safety and PK data from Cohorts C1 and C2 (Part 1) and there must be agreement that the current emerging safety, tolerability, and PK data support the start of dosing in Part 2.

Participants who were assigned to Cohorts A, B, C1, and C2 and who have completed Week 25 (Day 175) Visit in Part 1 will receive BIIB105 at 60 mg in Part 2. Participants who were

assigned to Cohorts D1 and D2 and who have completed Week 25 (Day 176) Visit in Part 1 will receive BIIB105 at 120 mg in Part 2. The 60 mg dose may be increased, at the Sponsor's discretion, to doses up to 120 mg. Before increasing the dose level, the SST must review safety and PK data for Cohorts D1 and D2 (Part 1) as described in the Dose Escalation Plan and there must be agreement that the current emerging safety, tolerability, and PK data support the dose increase. Doses in Part 2 may also be decreased at the Sponsor's discretion at any time during the study.

Participants who were assigned to Cohorts A, B, C1, and C2 will have a ≥16-week washout period between the time of their last dose of study treatment in Part 1 and their first dose in Part 2. Therefore, they will have a 4-week unblinded Loading Dose Period, during which they will receive 3 doses of BIIB105 administered every 2 weeks (on Days 1, 15, and 29).

Participants who were assigned to Cohorts D1 and D2 will not have had a washout period between their last dose of study treatment in Part 1 and their first dose in Part 2. Therefore, they will have a 4-week blinded Loading Dose Period, to protect the blind in Part 1. During this blinded Loading Dose Period, participants who received BIIB105 during Part 1 will receive two doses of BIIB105, on Days 1 and 29, and placebo on Day 15. Participants who received placebo in Part 1 will receive three doses of BIIB105 administered every 2 weeks (on Days 1, 15, and 29). Participants from Cohorts D1 and D2 must not receive their first dose in Part 2 sooner than 4 weeks after their last dose in Part 1.

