For all participants, the Loading Dose Period will be followed by an unblinded Maintenance Dose Period, where participants will receive maintenance doses of BIIB105 administered once every 4 weeks (up to approximately Week 156: either to Week 104, OR until the last participant enrolled has had the opportunity for their Part 2 Day 365 visit [Week 52], whichever occurs later). After the Maintenance Dose Period, participants will have an approximately 12-week follow-up period.

The SST will review safety and PK data from the extension cohorts at regular intervals.

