11.2.2. ALS Functional Rating Scale-Revised (standard)

The ALSFRS-R has been demonstrated to predict survival. The ALSFRS-R measures 4 functional domains, including respiratory, bulbar function, gross motor skills, and fine motor skills. There are 12 questions, each scored from 0 to 4, for a total possible score of 48, with higher scores representing better function [Cedarbaum 1999]. At each study site, the same qualified and trained study site staff member will consistently perform the ALSFRS-R for a participant. A qualified and trained backup ALSFRS-R rater will be identified in case the primary rater is unavailable. In Part 1, this study site staff member will remain blinded to participants' treatment assignments and to the results of other assessments. In Part 2, this study site staff member will remain blinded to participants' treatment assignments and to the results of other assessments during the blinded loading dose period for participants in Cohorts D1 and D2.

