15.1.5. Central Laboratories for Laboratory Assessments

A central laboratory has been selected by the Sponsor to analyze all hematology, coagulation testing, blood chemistry, and urine samples collected for this study, except for urine pregnancy tests and CSF, which will be analyzed by a local laboratory; repeat coagulation test will be analyzed by either the local laboratory or the central laboratory. A central laboratory will be utilized to test/confirm polyQ status for participation in Cohorts C2 and D2.

PK samples will be analyzed at a laboratory selected by the Sponsor. Duplicate PK samples will be collected in case the original sample is lost, damaged, or not evaluable.

The central laboratory will also receive, track, and ship all blood samples for specialized
genotyping, PK and PD biomarker analysis,
, and CSF samples for PK and PD biomarker analysis, including aliquots from these
samples, retained as backup in case original samples are lost or not evaluable. Residual blood
samples for future DNA testing will be processed to purify DNA and stored by the central
laboratory.
J

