4.1. Interim Analysis

There is no planned interim analysis for Part 1. However, as the data for Part 1 and Part 2 are in the same database, this is considered an interim lock.

Interim analysis of key safety, secondary, and [REDACTED] endpoints (including PK, PD, [REDACTED]) for Part 2 and integrated analyses based on unblinded data from Part 1 and interim data from Part 2 may be conducted; these will be discussed in a separate SAP.

The list of unblinding personnel and details of the unblinding procedure are provided in the 275AS101 Unblinding Plan. The study statistical programmers and biostatisticians will be unblinded following the interim lock. The BIIB105 275AS101 unblinded study team is listed in the Unblinding Plan. Participants, investigators and site staff and sponsor staff responsible for site monitoring and data management will remain blinded to Part 1 treatment assignments until Part 2 completes.

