ALSFRS-R total score = average of all answered item scores from other 3 domains x

Descriptive statistics

Descriptive statistics, including ALSFRS-R total and change from baseline in the ALSFRS-R total scores, will be evaluated by visit with descriptive statistics (mean, SD, median, 1st and 3rd quartiles, range) for pooled group DL and Part 2 BIIB105 60 mg in the FAS population.

Spaghetti plots will be presented by treatment group.

Statistical Analyses

The following analyses will be performed for pooled group DL in the FAS population.

CONFIDENTIAL

The information contained herein may not be used, disclosed, or published without the written consent of
Biogen MA Inc.

For integrated analyses of Part 1 and Part 2 for Cohorts D1 and D2, difference between treatment groups (i.e. Early-start BIIB105 120 mg and Placebo/Delayed-start BIIB105 120 mg) in least square means of Week 40 change from baseline with corresponding standard errors and 95% confidence intervals taken from the ANCOVA described in Section [5.6.1](#) based on the multiple imputation dataset.

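### In Part 2 the ALSFRS-R rater's blind to other assessment results is stated only for the loading period, although the early- versus delayed-start comparison continues beyond it

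*Protocol*

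**What the plan says.** **The rater rule.** In Part 1 the ALSFRS-R evaluator is blind to assignment and to the results of other assessments throughout (Protocol Table 2, footnote 22; Section 11.2.2). For Part 2, Table 3 footnote 18 says "For participants in Cohorts D1 and D2, during the blinded loading period, the evaluator should be blinded" to assignment and to other results. Section 11.2.2 repeats the limit: the rater stays blind to assignment "and to the results of other assessments during the blinded loading dose period for participants in Cohorts D1 and D2". The Part 2/integrated SAP reproduces footnote 18 in its own schedule. Section 11.2.2 also has the same staff member rate a given participant consistently.

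**Loading and maintenance.** For participants from D1 and D2, Protocol 5.3.2 says "they will have a 4-week blinded Loading Dose Period, to protect the blind in Part 1". Early-start participants receive placebo on Part 2 Day 15 for that purpose. Then "the Loading Dose Period will be followed by an unblinded Maintenance Dose Period".

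**Part 1 assignment.** Part 1 SAP 4.1 says that participants, investigators, site staff and certain sponsor staff "will remain blinded to Part 1 treatment assignments until Part 2 completes". Protocol 7.4 releases the randomization codes to investigators only once the study report is final.

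**The comparison.** Protocol Section 4 makes early versus delayed initiation part of a secondary objective for clinical function in the integrated analysis. For ALSFRS-R, the Part 2/integrated SAP (5.6.2) specifies the difference between groups "in least square means of Week 40 change from baseline with corresponding standard errors and 95% confidence intervals taken from the ANCOVA". Sections 5.6.3 and 5.6.4 name the same visit for HHD and SVC. Section 5.6.1 adds separate ANCOVA models with p-values at other visits, and 5.6.5 adds log-rank and Cox comparisons of the same two groups.

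**CSF results.** Protocol 15.1.5 sends samples to a central laboratory "except for urine pregnancy tests and CSF, which will be analyzed by a local laboratory". Under 9.2 the CSF panel includes white cell count and protein.

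**The concern.** ALSFRS-R is scored by a rater, so the randomised early- versus delayed-start contrast relies on that rater having no clue to the Part 1 arm. The sponsor evidently accepts this: the rule covers other results as well as assignment, and early-start participants receive an intrathecal placebo injection on Part 2 Day 15 to protect the Part 1 blind. The part of the rule about other results nevertheless has a stated end point, the end of loading. The one visit named for the comparison usually falls after that point, and so do later visits at which p-values may be produced.

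From then on, nothing in the protocol or SAPs stops the rater from reading a participant's CSF laboratory results, from either part. If those results carried information about who received active drug in Part 1, scores could drift differently in the two groups. Because one person rates the same participant over time, anything learned would carry forward to later visits.

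**Working it through.** **1. The SAP's visit mapping.** Part 2/integrated SAP 3.1 sets the target day for week w at 7w + 1, with a window from 7w − 12 to 7w + 15 for endpoints assessed every 4 weeks.

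- Week 28: Day 197 (184 to 211)
- Week 32: Day 225 (212 to 239)
- Week 36: Day 253 (240 to 267)
- Week 40: Day 281 (268 to 295)

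These agree with the SAP's table. The last Part 1 dose is on Day 169, and Protocol 5.3.2 requires at least 4 weeks before the first Part 2 dose. The earliest on-schedule Part 2 Day 1 is therefore 169 + 28 = Day 197, which is Week 28.

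**2. Week 40 against the end of loading.** With Part 2 Day 1 on study day s, Week 40 is Part 2 Day 281 − s + 1, and the last loading dose (Part 2 Day 29) is on study day s + 28.

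| Part 2 starts at | s | Week 40 in Part 2 days | Last loading dose, study day | Gap to Day 281 |
|---|---|---|---|---|
| Week 28 | 197 | Day 85 | 225 | 56 days |
| Week 32 | 225 | Day 57 | 253 | 28 days |
| Week 36 | 253 | Day 29 | 281 | 0 days |

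The third column reproduces the SAP's mapping table. With a Week 28 start, two ALSFRS-R visits up to and including Week 40 (Part 2 Days 57 and 85) fall outside the rater rule. With a Week 32 start it is one (Day 57), and with a Week 36 start none.

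**3. Which blind is stated for which period (ALSFRS-R rater, D1 and D2).**

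| Period | Part 1 assignment | Results of other assessments |
|---|---|---|
| Part 1 | Blind (Table 2 fn 22; 11.2.2) | Blind (same) |
| Part 2 loading | Blind (Table 3 fn 18; 11.2.2) | Blind (same) |
| Part 2 maintenance | Blind (Part 1 SAP 4.1; codes held under Protocol 7.4) | No statement |

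Only the last cell is empty. The assignment entry beside it comes from a different document than the rater rule, whose own wording stops at loading.

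**4. Illustration of size, on assumptions the documents do not supply.** Take the planned numbers, 36 + 12 = 48 early-start and 12 + 6 = 18 delayed-start, with no loss by Week 40, no true effect, a two-sided 5% test and a normal approximation. Then SE = SD × √(1/48 + 1/18) = 0.276 × SD.

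| Assumed SD of change | SE | Two-sided error, bias 0.5 point | Two-sided error, bias 1.0 point |
|---|---|---|---|
| 6 | 1.66 | 6.0% | 9.3% |
| 8 | 2.21 | 5.6% | 7.4% |
| 10 | 2.76 | 5.4% | 6.5% |

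The SD range and both bias values are assumed.

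**The case against.** The strongest reply is that the Part 1 arm stays concealed in any case. Part 1 SAP 4.1 and Protocol 7.4 both say so, and in maintenance everyone from D1 and D2 is planned to receive open-label 120 mg. Calling that period unblinded can therefore describe current treatment without disclosing Part 1 assignment. The loading-only wording may exist simply because loading is when the two groups receive different Day 15 injections. This stands. A reader might infer that the rater is unblinded to assignment after loading, but the documents do not support that; they support only a need to align the wording.

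A reader might also infer that CSF results reveal the arm. No passage says that CSF cell counts or protein are treatment-related or separate the groups. The SAPs tabulate CSF threshold exceedances and shifts as safety summaries. Local analysis puts results at the site, not necessarily in front of the certified evaluator. Part 1 CSF results arose while that evaluator was under the full rule, and by Part 2 Day 85 treated participants in both groups are on 120 mg, so contemporaneous values should be less informative. Operational blinding detail sits in an Unblinding Plan that is not available here. All of this limits the concern, but none of it supplies the missing rule.

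Two further readings go too far. Week 40 is the only named visit for the ALSFRS-R comparison, not the only test: p-values at other visits and time-to-event comparisons are planned too. And Day 85 is not fixed, since a Week 36 start puts Week 40 inside loading.

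Finally, Week 40 is named in an SAP dated 5 September 2024, written after early termination for an abbreviated report, and clinical function is a secondary endpoint. A wording change cannot alter ratings already collected.

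**Conclusion.** The point holds in a limited form. For Cohorts D1 and D2, the rule that keeps the ALSFRS-R rater from seeing other assessment results stops at the end of loading, and no passage extends it. Week 40 falls 56 days after the last loading dose for a Week 28 start, 28 days after for a Week 32 start, and on it for a Week 36 start. The loading-only wording on assignment also needs reconciling with Part 1 SAP 4.1.

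Whether any bias follows cannot be settled from the documents. It would require the rater to look at the results and the results to carry information about the Part 1 arm, and neither is shown. The 5.4% to 9.3% range illustrates what an assumed bias would do; it is not an estimate for this trial. This is an inexpensive strengthening of the plan, not evidence that the comparison is invalid.

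**What to change.** In Table 3 footnote 18 and in Section 11.2.2, for Cohorts D1 and D2, replace the loading-period limit with *throughout Part 2*. State that the rule covers the Part 1 assignment, consistent with Part 1 SAP 4.1, and the results of other assessments, including CSF laboratory results. Carry the same footnote into the schedule in the Part 2/integrated SAP. Covering all of Part 2 rather than stopping at Week 40 fits the plan for p-values at other visits.

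The cost is two changes of protocol wording. The same evaluators already work under this rule in Part 1 and in loading, so no extra staff or procedure is needed. The small downside is that the evaluator may not also review that participant's CSF results during maintenance.

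Extending the rule to the SVC and HHD assessors is optional; Sections 11.2.1 and 11.2.6 state no rule on other results for them. For ratings already collected, the report could say whether ALSFRS-R raters had access to CSF results after loading.
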